16.0 PUBLICATION POLICY

Investigator's right to publish study results is addressed in the clinical trial agreement between Investigator and Sponsor.

2. The K₃EDTA tubes should be kept cold and centrifuged as soon as possible after collection. Place the tubes on wet ice until the samples can be centrifuged. Centrifuge the samples at 1800 to 2000 times gravity (at 4°C if possible) for 15 ± 2 minutes. Immediately transfer the resulting plasma as follows:
 - Transfer the plasma equally between the 2 pre-chilled plastic transfer tubes. Carefully remove the plasma from the cells, avoiding contamination of plasma with white cells or platelets, since these may contribute enzymes that will falsely elevate measurements. Tubes should be appropriately labeled using labels supplied by the Sponsor.
 - The **plasma must be stored frozen at -70°C** or colder ideally within 30 minutes of collection. If necessary, samples can be stored on slushy ice for up to but not exceeding 4 hours. Samples should **never** be stored at -20°C. In addition, thawing and re-freezing can also lead to ex vivo cleavage of complement components and spurious production of activation products. Therefore, samples cannot be allowed to thaw until analysis. Samples are to be assayed on the first thaw.
 - All deviations to the collection procedures should be recorded and be included in the documentation with the sample shipment to the analytical laboratory.
 - All shipping instructions will be provided in a separate laboratory manual.

CAUTION! Samples for complement testing are sensitive to cold inactivation. Samples must be stored at -70°C or colder.

One set of plasma samples for each subject will be shipped frozen on dry ice to the analytical laboratory using shipping containers supplied by the Sponsor. The other set of samples will be stored frozen at -70°C or below and shipped to the laboratory following the schedule/instructions provided in the laboratory manual.

All samples will be analyzed within the established stability for the samples and will be properly disposed of after they have exceeded their established stability.

APPENDIX II: RECOMMENDED PROCEDURES FOR SUSPECTED VENOUS THROMBOEMBOLISM OR OTHER THROMBOTIC OR THROMBOEMBOLIC EVENTS

SAP	statistical analysis plan

SD	standard deviation
SOC	system organ class
TEAE	Treatment-emergent adverse event
VAS	Visual analogue scale
WBC	white blood cell
WHO	World Health Organization

1. INTRODUCTION

This Statistical Analysis Plan (SAP) provides a technical and detailed elaboration of the statistical analyses of safety and efficacy data as described in the final study protocol [Amendment 4](#) dated 26 January 2015. Specifications for tables, figures, and listings are also contained in this document.

2. STUDY DESIGN

2.1 General Study Design

This is a phase 3, multicenter, randomized, single-blind, dose-ranging, crossover study to evaluate the safety and efficacy of intravenous administration of CINRYZE[®] (C1 esterase inhibitor [human]) for the prevention of angioedema attacks in children 6 to 11 years of age with hereditary angioedema.

Individual participation from screening through the completion of the 1-month safety follow-up visit will be approximately 10 months (1-day screening visit, 12-week baseline observation period, two 12-week treatment periods [consecutive without any washout between treatment periods], and 1-month post-treatment safety follow-up visit). The study design is shown in [Figure 1](#).

[figure not shown]
CINRYZE (500 U or 1000 U) will be administered by IV injection twice weekly (every 3 or 4 days) for 12 weeks in two crossover treatment periods.

Participants in this crossover study are expected to receive both treatments (A = 500 U and B = 1000 U), assigned in random order, in sequential treatment periods. Each treatment period will be 12 weeks, without a washout between the two periods. Eligible subjects will be randomized to one of two treatment sequences, A/B or B/A.

- **Treatment sequence A/B**: CINRYZE at a dose of 500 U/1000 U IV twice weekly
- **Treatment sequence B/A**: CINRYZE at a dose of 1000 U/500 U IV twice weekly

This multicenter, randomized, single-blind, dose-ranging, crossover study will be conducted in multiple countries including the United States, Europe and Latin America. Other countries may be added if necessary to complete enrollment.

Figure 1: Study Design Flow Chart

Potential subjects (≥ 6 to < 12 years of age) will have a screening evaluation the day prior to entering the study's baseline observation period. Subjects with qualifying angioedema attack rates, and who meet all other eligibility criteria, will be enrolled and enter the observation period for at least 12 weeks.

2.2 Randomization

Twelve subjects will be randomized to one of two treatment sequences, with each sequence consisting of two 12-week treatment periods. Randomization will occur on Dosing Day 1 (Visit 1a) of Treatment Period 1. Each investigative site will receive a randomization schedule which will be used to assign subjects at that site to one of two sequences (A/B or B/A), with equal probability. Treatment A will be 500 U CINRYZE administered intravenously twice weekly (every 3 or 4 days) for 12 weeks and Treatment B will be 1000 U CINRYZE administered intravenously twice weekly (every 3 or 4 days) for 12 weeks.

2.3 Blinding

This is a single-blind study. Subjects and parents/caregivers will be blinded to the treatment administered. Study site personnel, qualified home healthcare professionals, and the Sponsor will not be blinded to dose and treatment sequence.

To maintain the treatment blind (for subjects and parents/caregivers), each dose of study drug will consist of a single IV injection (total volume of 10 mL).

2.4 Schedule of Assessments

Study assessments are presented in [Table 1](#), [Table 2](#), [Table 3](#), and [Table 4](#); blood collection time points for PK and post-treatment immunogenicity assessments are shown in [Table 5](#).

Table 1 Clinical Study Assessments – Screening and Baseline Observation Period

Procedures	Screening ^a	BASELINE OBSERVATION PERIOD (BY STUDY WEEK) ^b											
		1	2	3	4	5	6	7	8	9	10	11	12
Informed consent (written permission and assent)	X												
Medical/HAE history	X												
Prior/current medications ^c	X	X-----X											
Telephone contact ^d			X		X		X		X		X		X
Daily angioedema attack monitoring/eDiary ^e		X-----X											
EQ-5D-Y/eDiary ^f	X					X				X			

eDiary=electronic study diary; EQ-5D-Y (Youth version of EQ-5D)=health-related quality of life descriptive system for youth

^a All subjects will have a screening evaluation the day prior to entering Week 1 of the baseline observation period.

^b Additional weeks of observations will be considered at the discretion of the Investigator and Sponsor to allow a subject to qualify for randomization and entry into the treatment periods of the study. In this case, subjects will maintain the same schedule of assessments by beginning at Week 1 again for the additional weeks of observation (i.e., Week 13 = schedule of assessments for Week 1, Week 14 = schedule of assessments for Week 2, etc).

^c Parents/caregivers should record in the eDiary any medications taken by the subject for the management of angioedema attacks during the baseline observation period.

^d Study personnel will contact the parent/caregiver by telephone on Weeks 2, 4, 6, 8, 10, and 12 to discuss study compliance (completion of the eDiary daily) and to evaluate the subject's angioedema attack frequency. Telephone contacts will be documented in the source notes at the clinical site.

^e During the baseline observation period, parents/caregivers will use an eDiary to record the subject's symptoms or occurrences of angioedema attacks.

^f In addition, subjects should complete the EQ-5D-Y on each day that they experience signs or symptoms of an angioedema attack.

Table 2 Clinical Study Assessments – Treatment Period 1

Procedures	TREATMENT PERIOD 1 (BY STUDY WEEK) ^a											
	1	2	3	4	5	6	7	8	9	10	11	12
DOSING VISITS (1a to 24a)												

eDiary=electronic study diary; EQ-5D-Y (Youth version of EQ-5D)=health-related quality of life descriptive system for youth

^a Study drug administration and scheduled procedures will occur twice weekly (every 3 or 4 days) during the 12-week treatment period (Treatment Period 1, Visits 1a-24a).

^b Specified study procedures and blood samples should be performed/collected prior to study drug administration, on the same day.

^c Randomization will occur on Dosing Day 1 (Visit 1a) prior to the first dose of study drug in Treatment Period 1.

^d Medical history will be updated prior to randomization at Visit 1a. Physical examinations will be targeted based on reporting of adverse events and performed in accordance with standards at the site.

^e Vital signs will be measured using standard methods at each study site. On dosing days, vital signs should be obtained prior (within 60 minutes) to the injection of study drug and between 10 to 30 minutes after completion of the injection of study drug. Additional vital signs measurements may be performed if clinically indicated.

^f Body temperature should be measured prior to randomization at Visit 1a.

^g HIV (single assay antibody/Western Blot) and hepatitis (Hepatitis B Surface Antigen, Hepatitis C Antibody).

^h Pregnancy testing (urine) will be performed on females who have reached menarche.

ⁱ Study drug will be administered by qualified personnel to all subjects at the investigational site for Dosing Visits 1a, 12a, and 24a.

^j For those subjects who are dosed by a qualified home healthcare professional, study personnel will contact the parent/caregiver by telephone on Weeks 3 and 9 (after Dosing Visits 6a and 18a, respectively) to discuss and document study compliance, tolerability of CINRYZE dose, and adverse events. All telephone contacts will be documented in the source notes at the clinical site.

^k In addition, subjects should complete the EQ-5D-Y on each day that they experience signs or symptoms of an angioedema attack.

See Schedule 4 for details regarding clinical assessments at early discontinuation (if applicable), 1-week post-treatment, and 1-month post-treatment follow-up visits.

In the event a subject prematurely discontinues from treatment and/or the study, Early Discontinuation Visit procedures will be performed as soon as possible.

Note: Investigators will report all SAEs to Shire ViroPharma Drug Safety through 30 days after the last dose of study drug and SAEs considered related to study drug >30 days after the last dose of study drug.

Procedures	TREATMENT PERIOD 2 (BY STUDY WEEK) ^a																							
	1		2		3		4		5		6		7		8		9		10		11		12	
	DOSING VISITS (1b to 24b)																							
	1b	2b	3b	4b	5b	6b	7b	8b	9b	10b	11b	12b	13b	14b	15b	16b	17b	18b	19b	20b	21b	22b	23b	24b
Physical exam ^b	X _d											X												X
Body Weight	X _d																							
Concomitant medications	X	X	X	X	X	X	X	X	X	X	X	X	X	X	X	X	X	X	X	X	X	X	X	X
Vital signs (BP, HR) ^c	X			X		X		X		X		X		X		X		X		X		X		X
Clinical safety lab testing (hematology, chemistry, coagulation)	X _d											X												X
Study drug administration	X ^e	X	X	X	X	X	X	X	X	X	X	X ^e	X	X	X	X	X	X	X	X	X	X	X	X ^e
Telephone contact ^f						X												X						
EQ-5D-Y/eDiary ^{g, h}	X _d								X								X							
Daily angioedema attack monitoring/eDiary ^h	X-----X																							
Adverse events	X-----X																							
PK/PD assessments	Details on timing of blood sample collection for PK/PD assessments is provided in Schedule 5.																							
Immunogenicity testing (C1 INH antibody)	X _d																							

eDiary=electronic study diary; EQ-5D-Y (Youth version of EQ-5D)=health-related quality of life descriptive system for youth

^a Study drug administration and scheduled procedures will occur twice weekly (every 3 or 4 days) during the 12-week treatment period (Treatment Period 2, Visits 1b-24b).

^b Physical examinations will be targeted based on reporting of adverse events and performed in accordance with standards at the site.

^c Vital signs will be measured using standard methods at each study site. On dosing days, vital signs should be obtained prior (within 60 minutes) to the injection of study drug and between 10 to 30 minutes after completion of the injection of study drug. Additional vital signs measurements may be performed if clinically indicated.

^d Specified study procedures and blood samples should be performed/collected prior to study drug administration, on the same day.

^e Study drug will be administered by qualified personnel to all subjects at the investigational site for Dosing Visits 1b, 12b, and 24b.

^f For those subjects who are dosed by a qualified home healthcare professional, study personnel will contact the parent/caregiver by telephone on Weeks 3 and 9 (after Dosing Visits 6b and 18b, respectively) to discuss and document study compliance, tolerability of CINRYZE dose, and adverse events. All telephone contacts will be documented in the source notes at the clinical site.

^g In addition, subjects should complete the EQ-5D-Y on each day that they experience signs or symptoms of an angioedema attack.

^h If an angioedema attack is ongoing at Visit 24b, then recording of signs and symptoms and completing the EQ-5D-Y should continue daily until the attack resolves.

See Schedule 4 for details regarding clinical assessments at early discontinuation (if applicable), 1-week post-treatment, and 1-month post-treatment follow-up visits.

In the event a subject prematurely discontinues from treatment and/or the study, Early Discontinuation Visit procedures will be performed as soon as possible.

Note: Investigators will report all SAEs to Shire ViroPharma Drug Safety through 30 days after the last dose of study drug and SAEs considered related to study drug >30 days after the last dose of study drug.

Table 4 Clinical Study Assessments – Early Discontinuation, 1-week Post-treatment, and 1-month Post-treatment Follow-up Visits

Procedures	Early Discontinuation Visit ^a	1-Week Post-treatment Visit ^b	1-Month Post-treatment Follow-up Visit ^c
Concomitant medications	X	X	
Brief physical examination ^d	X	X	
Vital signs (BP, HR) ^e	X	X	
Clinical safety lab testing (hematology, chemistry, coagulation)	X	X	
Pregnancy testing ^f	X	X	
EQ-5D-Y	X	X	
Adverse events	X	X	
Immunogenicity testing (C1 INH antibody)	X	X	X
Virology testing ^g	X	X	

EQ-5D-Y (Youth version of EQ-5D)=health-related quality of life descriptive system for youth

^a Early discontinuation visit will be performed as soon as possible in the event a subject prematurely discontinues from treatment and/or the study. For those subjects who discontinue prematurely from treatment, every effort should be made to complete protocol evaluations for the 1-month post-treatment follow-up visit.

^b 1-Week post-treatment visit will be performed at the investigational site 1 week (±2 days) after the last dose of study drug.

^c 1-Month post-treatment follow-up visit will be performed 30 (±2) days after the last dose of study drug.

^d Physical examinations will be targeted based on reporting of adverse events and performed in accordance with standards at the site.

^e Vital signs will be measured using standard methods at each investigational site.

^f Pregnancy testing (urine) will be performed on females who have reached menarche.

^g HIV (single assay antibody/Western Blot) and hepatitis (Hepatitis B Surface Antigen, Hepatitis C Antibody).

Note: Investigators will report all SAEs to Shire VIROPHARMA Drug Safety through 30 days after the last dose of study drug and SAEs considered related to study drug >30 days after the last dose of study drug.

Table 5 Blood Sample Collection for PK/PD and Post-treatment Immunogenicity Assessments	
TREATMENT PERIOD 1	
Visit / Dose #	Blood Sampling Time Points
	C1 INH Antigen, C1 INH Function, Complement C4
1a / Dose 1	Pre Dose 1
	1 h post Dose 1 (\pm 15 min)
12a / Dose 12	Pre Dose 12
	1 h post Dose 12 (\pm 15 min)
24a / Dose 24	Pre Dose 24
	1 h post Dose 24 (\pm 15 min)
	2 h post Dose 24 (\pm 15 min) – optional sampling time point
	4 h post Dose 24 (\pm 15 min) – optional sampling time point
	8 h post Dose 24 (\pm 15 min) – optional sampling time point
TREATMENT PERIOD 2	
Visit / Dose #	Blood Sampling Time Points
	C1 INH Antigen, C1 INH Function, Complement C4
1b / Dose 1	Pre Dose 1
	1 h post Dose 1 (\pm 15 min)
12b / Dose 12	Pre Dose 12
	1 h post Dose 12 (\pm 15 min)
24b / Dose 24	Pre Dose 24
	1 h post Dose 24 (\pm 15 min)
	2 h post Dose 24 (\pm 15 min) – optional sampling time point
	4 h post Dose 24 (\pm 15 min) – optional sampling time point
	8 h post Dose 24 (\pm 15 min) – optional sampling time point

Note: If a subject presents to the investigational site with an angioedema attack, every effort should be made to

Table 5 Blood Sample Collection for PK/PD and Post-treatment Immunogenicity Assessments	
obtain a PK blood sample prior to any treatment. In addition, if the subject is treated with commercial C1 INH, every effort should be made to obtain a 1-hour post-treatment sample. These samples will be analyzed for C1 INH antigen and functional C1 INH activity.	
POST-TREATMENT	
Visit	Blood Sampling Time Points
	Immunogenicity (C1 INH antibody)
1-week post-treatment	1 week (\pm 2 days) after the last dose of study drug
1-month post-treatment	30 (\pm 2) days after the last dose of study drug

2.5 Determination of Sample Size

This study is designed to assess the safety, tolerability, and relative efficacy of two different doses (500 U and 1000 U) of CINRYZE as prevention therapy for angioedema attacks in children 6 to 11 years of age with HAE. Twelve subjects will be randomized in this study. Given the limited number of pediatric subjects with HAE who will fall within this age category and have a history of angioedema attacks appropriate to meet study inclusion criteria (Caballero, 2012), this number is considered a reasonable target with respect to the ability to enroll eligible subjects.

3. OBJECTIVES

3.1 Primary Objective

To assess the relative efficacy of two dose levels of CINRYZE (500 U and 1000 U) administered by intravenous (IV) injection every 3 or 4 days to prevent angioedema attacks in children 6 to 11 years of age.

3.2 Secondary Objective

- To assess the safety and tolerability of two dose levels of CINRYZE administered by IV injection in children 6 to 11 years of age with hereditary angioedema (HAE).
- To characterize the pharmacokinetics (PK) and pharmacodynamics (PD) of CINRYZE administered by IV injection in children 6 to 11 years of age.
- To assess the immunogenicity of CINRYZE following IV administration.

3.3 Other Objective

To assess the impact of treatment on health status (quality of life) in children 6 to 11 years of age with HAE.

4. SUBJECT POPULATION SETS

For all assessments, the treatment used will be the actual treatment and will be assigned according to the treatment period in which the assessment is performed.

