11. SAFETY ANALYSES

The safety analyses will be performed by treatment using the Safety Set. Safety endpoints include AEs, clinical laboratory variables, vital signs, and C1 INH antibody variables. For each safety variable, the last value collected prior to the first dose of the investigational product will be used as baseline for all analyses of that safety variable.

Summary statistics and changes from baseline to post-baseline for laboratory testing and vital signs by dose group will be presented. Adverse events by dose group, by dose group (dose normalized to body weight [U/kg]), and by time of onset (e.g., during administration of study drug or within 24 hours after the end of injection of study drug) will be summarized. Results of C1 INH antibody testing will be reported for individual subjects and summarized as appropriate.

Final on Treatment Assessment (LAoT) will be defined as the last observation recorded within the period in which the treatment is administered.

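### Read by visit, the period rule in SAP Section 4 puts the pre-dose Visit 1b labs and EQ-5D-Y under a dose not yet given and makes a week-6 lab the final Period 1 value in the shift tables

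*SAP*

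**What the plan says.** SAP Section 4 gives a single rule that covers every assessment: "the treatment used will be the actual treatment and will be assigned according to the treatment period in which the assessment is performed". It sets no date or clock boundary between the periods.

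The periods are defined explicitly only in the schedule footnotes of SAP Section 2.4. Footnote a for Period 1 places dosing and procedures "during the 12-week treatment period (Treatment Period 1, Visits 1a-24a"; the matching footnote for Period 2 reads "during the 12-week treatment period (Treatment Period 2, Visits 1b-24b". Visit 1b is thus the first visit of Period 2.

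The Visit 1b safety labs, EQ-5D-Y and C1 INH antibody sample all carry footnote d: "Specified study procedures and blood samples should be performed/collected prior to study drug administration, on the same day". Protocol Section 3.0 has no washout.

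Protocol 6.5 and SAP 11.2 give the same safety lab visits: 1a pre-dose, 12a, 1b pre-dose, 12b, 24b and 1 week post-treatment. Neither lists 24a.

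SAP Section 11 sets the safety baseline: "the last value collected prior to the first dose of the investigational product will be used as baseline for all analyses". It defines LAoT as "the last observation recorded within the period in which the treatment is administered". SAP 11.2 uses LAoT for the lab shift tables (Tables 4.6.8 to 4.6.10). The VAS baseline in SAP 13.1 is averaged over the observation period.

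**The concern.** At Visit 1b, before dosing, a completer has had 24 scheduled doses of the Period 1 treatment and none of the Period 2 treatment. What is measured then reflects the Period 1 dose. A period rule tied to visit numbers files it under the other dose. Because neither the lab baseline nor the VAS baseline is taken from Visit 1b, the value would be tabulated as a result under the new dose, not as that dose's starting point.

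The shift tables have a related problem. The lab that closes Period 1 is collected, but on this reading it belongs to Period 2. The LAoT for Period 1 falls back to mid-period.

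Safety and tolerability of the two dose levels is a secondary objective. A lab change arising in the second half of Period 1 would be missing from the shift table for the dose that preceded it, and in the by-time-point table it would stand in the other dose's column.

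**Working it through.** **Inputs.** Two doses a week, 3 or 4 days apart, 24 doses per 12-week period, no washout (Protocol 3.0 and 5.2). Lab visits from Protocol 6.5 and SAP 11.2. Period and LAoT definitions from SAP 2.4 and 11. Assumptions: full completion, scheduled labs only, and alternating 3- and 4-day intervals so that 24 intervals fill 12 weeks (12 × 3 + 12 × 4 = 84 days).

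1. **The plan's own dose-to-week figures.** Week = dose number ÷ 2, rounded up. Dose 6: 6 ÷ 2 = 3. Dose 18: 18 ÷ 2 = 9. Both agree with the telephone-contact weeks in Protocol 3.0. By the same rule dose 12 falls in week 6 and dose 24 in week 12.

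2. **Labs sorted by visit.** Period 1 holds 1a pre-dose and 12a, so LAoT = 12a. Period 2 holds 1b pre-dose, 12b and 24b, so LAoT = 24b.

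3. **Timing of the two LAoT labs.**
   - 12a is 11 intervals after 1a: 6 × 3 + 5 × 4 = 38 days, or 5 × 3 + 6 × 4 = 39 days.
   - 24b is 23 intervals after 1b: 12 × 3 + 11 × 4 = 80 days, or 11 × 3 + 12 × 4 = 81 days.

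4. **What the shift tables miss in Period 1.** 84 − 39 = 45 to 84 − 38 = 46 days. In doses, 24 − 12 = 12 of 24, or half. If the 13 intervals from 12a to 1b were all 3 or all 4 days, the gap would be 39 or 52 days.

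5. **Values in the Visit 1b row.** One lab panel and one scheduled EQ-5D-Y per subject reaching 1b: 12 of 12 with full completion, and 6 per dose column at a 6/6 split.

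6. **Effect on the dose comparison at 6/6.** Each dose column takes six Period 1 and six Period 2 LAoT values. Using midpoints, the mean LAoT day is (6 × 38.5 + 6 × 80.5) ÷ 12 = 59.5 in both columns. Both lose the same late-period information.

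7. **If pre-dose 1b is credited to Period 1.** It is 24 intervals after 1a, so day 84, after all 24 doses. The Period 1 LAoT moves from day 38 to 39 to day 84. The remaining difference from Period 2 is 84 − 81 = 3 to 84 − 80 = 4 days.

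The absence of a 24a lab rests on the two matching visit lists. The lab row of Protocol Schedule 2 and the grid of SAP Table 2 are not legible enough in the available text to confirm it.

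**The case against.** The best defence is that the footnotes schedule visits and do not define analysis windows. SAP 10.1 and 11.1 take the period-specific weight before the period's first dose, and Protocol 7.3 counts time to first attack from that dose. Both hint that a period begins at its first dose. This stands in part: a reader might infer that the SAP certainly credits Visit 1b values to the wrong dose, and the documents do not go that far. But SAP 4 and 11 do not adopt a first-dose boundary for labs or EQ-5D-Y, and the visit definitions are the only explicit ones.

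Other stronger readings also fail:

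- **That Period 2 never closes for labs, so the 1-week lab could be its LAoT.** The visit definition ends Period 2 at 24b, SAP Table 4 labels the 1-week visit as post-treatment, and LAoT must fall within the period.
- **That the comparison between doses is biased.** At 6/6 it is not. SAP 2.2 says "Each investigative site will receive a randomization schedule which will be used to assign subjects at that site to one of two sequences" and states no overall balance, so 6/6 is an assumption. An uneven split would separate the mean LAoT days, but nothing in the documents ties such a gap to any conclusion.
- **That late Period 1 labs are lost.** They remain in the by-time-point tables, where Visit 1b is identifiable as pre-dose. SAP 18.3 uses all post-baseline values for the potentially clinically important (PCI) determination, and the listings show every result.

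Two uncertainties remain. The titles of Tables 4.6.8 to 4.6.10 do not mention treatment; dose columns follow from the general statement in SAP 11 that safety is analysed by treatment. And SAP 13.1 presents VAS change at post-dose visits without saying whether pre-dose Visit 1b counts as one, although Tables 3.6.1 and 3.6.2 are by treatment and scheduled visit.

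**Conclusion.** The point holds in limited form. Applied as written, with periods read by visit, the SAP tabulates the pre-dose Visit 1b labs and EQ-5D-Y under the dose about to start. A completer's scheduled Period 1 LAoT lab is then Visit 12a, about 38 to 39 days into 84, against 80 to 81 days for Period 2. No scheduled lab reflecting Period 1 doses 13 to 24 reaches the shift tables, although one is collected.

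This rests on the visit-based reading, on completion of both periods and on scheduled labs only. An unscheduled lab after 12a would replace it for that subject, and subjects who stop early have their own discontinuation lab.

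The consequence is confined to descriptive safety and EQ-5D-Y tables. The primary attack count comes from daily diary records and uses neither LAoT nor the Visit 1b labs or EQ-5D-Y. The rule should be corrected, but the trial's main conclusion does not depend on it.

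**What to change.** In SAP 4 and 11, state that for safety labs, EQ-5D-Y and the C1 INH antibody sample, Period 1 runs until the start time of the first Period 2 dose. Then:

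- Credit the pre-dose Visit 1b values of these three to the Period 1 treatment.
- Take the Period 1 LAoT lab from Visit 1b pre-dose.
- Keep the Period 2 LAoT lab at Visit 24b, and treat the 1-week lab as post-treatment.

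Three uses of Visit 1b pre-dose should stay with Period 2: the period-specific weight baseline (SAP 10.1 and 11.1), the reference for the pre- to post-dose change in C1 INH and C4 (SAP 10.3), and the first of the paired vital signs. SAP Table 3 specifies that pair around each injection: "vital signs should be obtained prior (within 60 minutes) to the injection of study drug and between 10 to 30 minutes after completion".

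The cost is one derivation rule with three exceptions, so data from one visit sit under two treatments. No new visit or sample is needed; infusion start times are already recorded (Protocol 5.3). A timing difference of 3 to 4 days between the two LAoT labs remains.
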